We are working with staff members at The Mighty who have agreed to implement the study. At no point will they send us data that may compromise the identity of the research participants. The technology team at TheMighty will manage the platform, administer the surveys, and store the data. They have had extensive experience in surveying their users prior to this research project.

3.3 Are there any other additional study staff whose role in this study requires special qualifications in addition to ethics training (e.g., licensed clinical psychologist, phlebotomist, etc.)?

Yes (see below)

No

*If "Yes" describe:*

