The protocol for the actual research trial is nearly identical to the feasibility trial described above. We will recruit 500 patients total during the research trial. Patients will be randomized to either the AT or Control condition, with approximately 50% of the sample in each condition. Based on the results of the feasibility trial, we may adjust parameters in order to maximize meaningful engagement. Such parameters may include the number of articles sent, frequency of sending articles, timing of when articles are sent, etc. Additionally, all patients will receive a follow-up survey at 2 weeks after the 5-14 day intervention period in order to assess whether the effect of reading articles is sustained. These follow-up surveys will assess similar constructs to those assessed at baseline and during the intervention period. One week following administration of the follow-up surveys, participants in the Control condition will receive the same intervention (1 article assigned per day with pre- and post-article surveys) as those in the AT condition, as well as a final follow-up surveys 2 weeks after the intervention. The intent of this design is to allow those in the Control condition to also receive any benefits of the intervention.

***The below sections contain additional questions depending on the type of research that you are conducting and is meant to supplement the study overview. Please complete each section, as applicable.***

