## 6. RISK AND BENEFIT ASSESSMENT

6.1 Describe the foreseeable risks associated with your study. Please include discussion of any physical risks and non-physical risks, such as economic, psychological, social, and legal harms.

1. Asking subjects about suicide may cause distress in some patients.
2. Despite the fact that the articles selected by TheMighty decrease the level of suicidal ideation collectively, there may be certain subjects who experience increased SI after reading the assigned articles.
3. If there is mismanagement of data, user names and/or emails may be associated with their activity in the research database, and may become visible to the researchers

6.2 Describe the steps that you will take to minimize risks to your participants (for example, using pseudonyms or a coding system, etc.)

1. In order to address this concern, we will take several measures. First, during the consenting process, we will include language that warns subjects that some of the survey questions may induce distress. Second, we will make sure that subjects can easily exit the study at any time.

It is important to note that research has demonstrated that asking patients about suicide does not appear to increase the level of suicidality (Dazzi et al, 2014). The research team will meet regularly to review data and any adverse effects. [name], licensed clinical psychologist, will oversee these meetings.

2. At the end of each survey, we will provide users with a pop-up that provides information on how to get in touch with a suicide hotline.
3. We will institute an automatic data cleaning process that ensures that all names and emails will be deleted from the database before any researchers have access.

6.3 Are provisions needed for medical and/or psychological support resources (for example, in the event of research-related distress or incidental findings)?

Yes

No

6.4 If applicable, what steps will you take if a participant becomes distressed during your study or reports intent to harm themselves or others?

Should a participant report elevated suicidal ideation, a pop-up screen will be triggered and will provide contact information for a suicide hotline

6.5 Describe any potential direct benefits to participants in the study. If there are no individual benefits, indicate as such.

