## 7. CHARACTERISTICS OF THE STUDY POPULATION

7.1 Indicate the estimated number of participants, by subgroup if applicable. *If it is not possible to estimate the number of participants (e.g., open online survey), please indicate that it is not possible and provide an explanation of why it is not possible.*

For the initial feasibility trial, we will enroll 50 users in order to test out operations. After process optimization (adjusting timing of sending articles, number of articles sent, etc.), we plan to recruit a

total of 1000 participants for the RCT. Half (500 participants) will be randomized to the AT Condition, and half will be randomized to the Control Condition.

7.2 Describe the criteria for enrollment – Will you be limiting your enrollment to a certain age range, gender, people with certain health conditions, etc.? Please also describe any criteria that will exclude people from enrollment.

Enrollment Criteria: In order to qualify for the study, participants must report:

- having thought about suicide in the past 12 months, and
- that they are at least 18 years old
- English is primary language

Exclusion Criteria: Prospective participants will be excluded from the study if they report:

- a high level of suicide intent (as indicated by a 7 or greater on a 10-point scale of intent to act on suicidal thoughts)

7.3 Are there any potential vulnerable populations or individuals proposed for involvement in the research? (check all that apply)

- Children
- Wards of the State
- Prisoners/Detainees
- Pregnant Women
- Adults not Competent to Consent
- Non-English Speaking
- Employees of Harvard University (as a focus of the study)
- Undergraduate Students of Harvard University (as a focus of the study)
- Staff or students that are part of your lab or for whom you provide oversight
- Other – (see below):

*If “Other” please specify:*

---

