## 9. SCREENING

9.1 Will you be screening participants for eligibility? *Note that If you are using inclusion or exclusion criteria, you will be “screening” individuals in order to determine who is eligible.*

Yes

No (*skip to next section*)

9.2 Explain what your screening criteria will be and how you will conduct the screening process.

When new users access certain types of articles, a dialog box will appear asking them if they are interested in participating in a study aimed at helping The Mighty understand the impact of the articles posted by other users on its platform and asking if they would like more information. Prospective participants who respond “yes” will be prompted to fill out a brief screening survey to indicate their age and history of suicidal thoughts and behaviors.

9.3 Do you plan to destroy the data from people who participate in the screening process and do not qualify to be in the study as soon as the screening process is over?

Yes

No (*see below*)

***If “No” explain why you will keep the data collected in the screening process for people who are not eligible to participate in this study.***

We plan to destroy data from participants who participate in the screening process and do not qualify for the study after the enrollment has ended. However, we would like to retain screening data from the participants who do not qualify for the study to ensure that they do not attempt to re-enroll and provide false screening information at a later time.

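### The intent limit of 7 is applied at screening and, in the visible text, is not re-applied when Control participants start stories at day 26-35

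*Protocol*

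**What the plan says.** Protocol section 7.2 excludes prospective participants who report "a high level of suicide intent (as indicated by a 7 or greater on a 10-point scale of intent to act on suicidal thoughts". Section 9.2 describes a single brief survey, taken before enrolment. Section 9.3 keeps the answers of people who do not qualify "to ensure that they do not attempt to re-enroll and provide false screening information at a later time".

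For the Control arm, section 5.1 Part 2 says: "One week following administration of the follow-up surveys, participants in the Control condition will receive the same intervention". These stories come with surveys before and after each one. The follow-up that sets this clock is two weeks after the intervention period in 5.1 Part 2 and in the SAP (Hypothesis 2), but four weeks after it in section 5.3.

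On safety, section 6.1 accepts that "there may be certain subjects who experience increased SI after reading the assigned articles". Section 6.2 puts hotline information at the end of every survey and adds: "The research team will meet regularly to review data and any adverse effects". Section 6.4 says: "Should a participant report elevated suicidal ideation, a pop-up screen will be triggered and will provide contact information for a suicide hotline".

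**The concern.** The plan sets a level of intent above which a person should not enter a study that assigns stories about suicide. In the AT arm stories start at entry, so the check and the exposure almost coincide. In the Control arm they are weeks apart, and the start is set by the calendar alone. As written, a Control participant who has since moved to 7 or more is assigned stories, although the same answer at screening would have kept that person out. What is at stake is the safety of a few people at the start of a new exposure, in a population recruited for recent suicidal thoughts. The validity of the trial's main comparison is not in question.

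**Working it through.** The plan states no interval between screening and Control's first story, so there is no figure to reproduce. The interval follows from the plan's own timings.

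**Inputs**
- Intervention period L: 5 to 14 days (5.1 Parts 1 and 2).
- Delay to follow-up F: 14 days (5.1 Part 2; SAP Hypothesis 2), or 28 days (5.3).
- Delay from follow-up to Control's stories: 7 days (5.1 Part 2).
- Assumption: screening, consent and day 0 fall together. Any gap adds to the interval in both arms.

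**Formula:** start day = L + F + 7.

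| L | F | Control start |
|---|---|---|
| 5 | 14 | 5 + 14 + 7 = day 26 |
| 14 | 14 | 14 + 14 + 7 = day 35 |
| 14 | 28 | 14 + 28 + 7 = day 49 |
| 5 | 28 | 5 + 28 + 7 = day 40 |

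The first two rows use the follow-up that 5.1 and the SAP share, and they give the range to cite. The last two need the conflicting time in 5.3. The final row also carries T2 over to a 5-day period, although 5.3 defines it after a 14-day one.

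Cross-check: section 11.4 ends the AT arm at week 4, and 14 + 14 = 28 days agrees with the two-week follow-up. For Control, 35 + 14 + 14 = 63 days is week 9, against the stated week 8. That is a separate discrepancy and does not change this point.

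**What exists after screening, and whether it holds stories**

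| Measure | When | Holds stories? |
|---|---|---|
| Ideation items in the daily surveys (5.1) | Initial period | Not stated |
| Shortened SITBI-SR (5.2, 5.3) | T0, T1, T2 | Not stated |
| Survey before each story (5.1 Part 2) | Just before Control's first story | Not stated |
| Hotline information (6.2) | After every survey | No |
| Hotline pop-up (6.4) | On elevated ideation | No |
| Team meeting (6.2) | Regularly | No role in Control's start stated |

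Section 5.1 Part 1 lists the constructs in the survey around each story: optimism, connectedness, identification with the author, and ideation. Intent is not named there.

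**Size.** The Control arm is about 250 people (half of the 500 in 5.1 Part 2) or 500 (7.1). The documents give no share at 7 or more at Control's start. For scale only, each 1% would be 0.01 x 250 = 2.5 people or 0.01 x 500 = 5 people, and fewer after dropout. This converts a share into people; it does not estimate the share.

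**Effect on the analysis.** With a 14-day period, Hypothesis 1 uses data to day 14 and Hypothesis 2 uses day 14 + 14 = 28. Control's stories start at day 35, so a hold at that point cannot change either result.

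**The case against.** The strongest reply is that 7.2 is an entry criterion, and entry criteria are not ordinarily re-applied to people already enrolled. The plan gives no reason for the cut at 7. Section 9.3 covers everyone who fails screening for any reason, so it may be only a guard against false answers. An AT participant who reaches 7 on day 2 also keeps receiving stories. This stands to the extent that the plan does not break a rule of its own. But Control's first story is the start of a new exposure, which makes it a natural place to repeat the check. A mid-course hold in AT would change the exposure under test; a hold at Control's start would not.

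Second, monitoring continues, up to a survey immediately before the first story. That also stands, and a reader who infers that Control goes unmonitored would be wrong. What is missing is any answer that holds the stories.

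Third, the survey file and timeline diagram are not in the documents. The intent item, or even a hold, may be there. This limits the point to the visible text.

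Three further readings are tempting and not supported:
- That a check at Control's start guards against the harm named in 6.1. That harm is worsening after reading. The check measures intent before reading, so someone at 3 who then worsens passes it.
- That de-identification prevents a hold for one person. Section 6.2 says "all names and emails will be deleted from the database before any researchers have access", but this concerns researchers. In the study staff section, "The technology team at TheMighty will manage the platform, administer the surveys, and store the data", and the pop-up in 6.4 already responds to individual answers.
- That the meeting in 6.2 would stop a person's stories. The text gives it neither that power nor a role in Control's start.

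**Conclusion.** The point holds as a cheap safety improvement, with medium confidence. The intent limit of 7 is applied once, and Control's stories begin 26 to 35 days later with no stated re-application. A reader might cite 26 to 49 days as one range, but that mixes two conflicting follow-up times. The conclusion rests on the visible text and on entry following screening closely. The number of people affected is unknown and may be small. Hypotheses 1 and 2 are unaffected.

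**What to change.** In section 5.1 Part 2, include the screening intent item in the survey already planned before Control's first story. If the rating is 7 or more, the platform should:
- show the hotline pop-up;
- defer that person's assigned stories;
- send the same short survey again at a stated interval, for example daily or weekly;
- start the stories once the rating is below 7.

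The repeat survey has to be written in. In Control's story phase the surveys are attached to stories, so a person whose stories are held would otherwise have no means of being released.

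The cost is one survey item, one platform rule beside the existing pop-up trigger, and a repeat survey for the few people held. Nobody else in Control is delayed. The downside is that those held have study-assigned stories deferred, and the stories were chosen because they may help. They remain public on the site, so the hold stops only the study's own assignment. If the survey file already contains the intent item, only the hold and the repeat survey need adding.

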5.4 Will you be using any survey software (such as Qualtrics)?

Yes (see question below)  
 No

**If "Yes" which survey software will you be using? :**

We will use a survey tool built internally by TheMighty. This company has previously had extensive experience surveying their users about their experience on the website.

## INTERVIEWS/ORAL HISTORY/FOCUS GROUPS

*Skip this section if not applicable.*

5.5 Explain where interviews/focus groups will take place (including possible online venues such as Skype, online chat rooms, etc.)

5.6 Describe any steps you will take to protect the participant's privacy during the interview/focus group.

5.7 Describe the number of interviews/focus group sessions you anticipate for each participant and approximately how long you expect each interview/focus group to last.

#### OBSERVATIONAL/ETHNOGRAPHIC RESEARCH

*Skip this section if not applicable.*

5.8 If you will be actively participating in the field (as in participant-observation), describe what this will entail.

5.9 Describe what and who will be observed and in what settings (such as public events, religious ceremonies, household activities, work meetings, internet chat-rooms and social media sites, etc.)

5.10 Will any observational data be considered private, according to the standards of that community?

Yes **(see below)**  
 No

*If "Yes" describe the information that would be private.*

5.11 Will the data you collect contain any information that identifies specific individuals?

Yes  
 No

5.12 Do you plan to quote the remarks of participants in your study?

Yes  
 No

5.13 Will you notify participants that they are being observed?

Yes  
 No **(see below)**

*If "No" explain the circumstances why you would not be able to let participants know they are being observed.*

5.14 If permission to observe participants is obtained, how will you ascertain whether there are individuals who do not want to participate, and how you will manage such a situation?

**AUDIO-RECORDING/VIDEO-RECORDING/PHOTOGRAPHS**

*Skip this section if not applicable.*

5.15 What type of recording will take place? (check all that apply)

- Audio-Recording
- Video-Recording
- Photography
- Other *(see below)*

*If "Other" describe:*

5.16 Explain what types of data will be recorded or photographed.

5.17 If you will be collecting sensitive data, will you use any procedures to de-identify or anonymize the recordings or photographs?

5.18 Explain what will happen to the recordings/photographs at the end of the study.

**DECEPTION AND INCOMPLETE DISCLOSURE**

*Skip this section if not applicable.*

***Deception is the intentional misleading of a subject about the nature of the study. While withholding of full information is known as incomplete disclosure.***

5.19 Describe what information will be withheld from participants or what misinformation will be provided to participants.

5.20 Explain why this research involves no more than minimal risk to participants and why it would be impracticable to carry out the research without the use of deception or incomplete disclosure.

5.21 Describe the plans for debriefing participants after their participation. If you do not plan to debrief participants, explain why.

***Please be sure to attach a copy of the debriefing script (if applicable) to the “Local Sites Documents” section in the ESTR SmartForm.***

## USING PREVIOUSLY COLLECTED DATA

*Please complete this section if you are receiving data that has already been collected. This section does not pertain to data that is being collected through interaction or intervention as part of this study. Skip this section if not applicable.*

5.22 Indicate the identifiability of the data:

- Will not contain any direct or indirect identifiers; will be anonymous.
- Will not be directly identifiable, but there will be a code held by the data source that links to the identities; will be coded.
- Will contain direct or indirect identifiers, but this research team will remove them upon receipt; will be de-identified data.
- Will contain direct identifiers; will be identifiable.

5.23 Describe which data sets you plan to analyze, who is providing the data to you, and whether the data are public use data sets, restricted access datasets, or another type of dataset.

The data set from The Mighty will include characteristics of users including IP address, time spent on the page, articles viewed, and location (city, state, and country). If the user is a registered on The Mighty platform, we can gather additional information available through The Mighty, such as their self-stated interests and history of viewed articles.

5.24 Provide an overview of the types of variables that are contained in the dataset (for example, identifiable data such as names, dates of birth, addresses, or any data that are considered sensitive).

Secondary data will be used. Variables include information that users have filled out in their TheMighty account, which includes age, gender, geographical location, and prior activity on TheMighty website. The users' names will be deleted from the research analyses in order to protect privacy.

5.25 Was the data you plan to analyze collected in a previous research study?

Yes (see below)

No

***If "Yes" provide the title/name of the previous research study and which institution and researcher collected the data for the previous study. If the data were collected in a previous Harvard University research study, provide the ESTR number assigned to that study.***

5.26 Will any of your data be obtained from internet sites (including data mining and data scraping activities)?

Yes (see question below)

No

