***If "Yes" what websites will you access to obtain the data?***

***Please know that it is your responsibility to check the terms of service of any websites from which you plan to collect data to determine whether your planned data collection is compatible with the terms of service.***

Similar to other online social networks, TheMighty owns the user data and is therefore permitted to conduct research on the data. We will only conduct research using secondary data of individuals who have consented to being part of the study. The relevant language from the terms of service is copied below:

"USE OF CONTENT SUBMITTED BY YOU

BY UPLOADING, POSTING, SENDING OR SUBMITTING PHOTOGRAPHS, PICTURES, IMAGES OR ANY OTHER CONTENT INCLUDING, WITHOUT LIMITATION, GRAPHICS, VIDEO, DATA, TEXT, FILES, LINKS, SOFTWARE, MUSIC, SOUND ("CONTENT"), YOU ARE CONSENTING TO BE BOUND BY THESE TERMS OF USE. IF YOU DO NOT AGREE, DO NOT UPLOAD, POST, SEND OR SUBMIT ANY CONTENT TO THIS SITE.

You agree that any Content you upload, post, email, transmit or otherwise make available via the Service is non-confidential and that we shall have a perpetual, worldwide, non-exclusive license to use any such Content in connection with the Service and our business (and any successor), including without limitation for promoting and redistributing part or all of the Service (and derivative works thereof) in any media formats and through any media channels. You also hereby grant each User a non-exclusive license to access your Content through the Site, and to use, reproduce, distribute, prepare derivative works of, display and perform such Content as permitted through the functionality of the Site and under these Terms of Service. The submission of any materials to us irrevocably waives any and all "moral rights" in such materials, including the rights of paternity and integrity."

The full terms of service are here for your reference:

<https://intercom.help/themighty/en/articles/1781523-terms-and-conditions>

5.27 Is the data publicly available on the internet (i.e., freely available without permission, sign-in, or other restrictions)?

Yes

No

5.28 Do you plan to access any data that is Protected Health Information (PHI) under the HIPAA law (for example, data held by a hospital or other healthcare provider or insurer)?

Yes

No (*skip to question #5.31*)

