### ADULT PARTICIPANTS

*If you will not include adults in your study, please skip this section.*

10.1 Will you be obtaining informed consent or an agreement to participate (for Exempt studies) from participants that take part in your study?

Yes, I will be obtaining informed consent or an agreement to participate.  
 No, I will not be obtaining consent or an agreement to participate (**skip to next section after answering below**)

*If you will not be obtaining consent or an agreement to participate, please explain:*

- **why this research involves no more than minimal risk to participants and**
- **why it would be impracticable to carry out the research with consent or an agreement to participate**

Participants will consent to their data from their user profile in TheMighty to be linked with their survey responses.

10.2 Will the consenting or an agreement to participate process involve obtaining a signature?

Yes  
 No (**see below**)

*If a signature is not obtained, explain why:*

The proposed study will be conducted online, so a physical signature is not feasible. An electronic consent form will be used instead.

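### The protocol promises that no identity-compromising data will be sent, yet its platform data set includes IP address and city, and the stated cleaning step covers neither

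*Protocol*

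**What the plan says.** The relevant statements are spread over several parts of the protocol.

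- **Section 3, just before item 3.3**, on the platform's staff: "At no point will they send us data that may compromise the identity of the research participants". The same paragraph says the platform manages the site, runs the surveys and stores the data.
- **Item 5.23**, on the data set supplied by the platform: it will include "characteristics of users including IP address, time spent on the page, articles viewed, and location (city, state, and country"). For registered users, stated interests and viewing history may be added.
- **Item 5.24**: the variables from the user's account include "age, gender, geographical location, and prior activity on TheMighty website". The safeguard given there is that users' "names will be deleted from the research analyses in order to protect privacy".
- **Item 5.26**: "We will only conduct research using secondary data of individuals who have consented to being part of the study".
- **Item 6.1, third risk**: if data are mishandled, user names or emails could be tied to activity in the research database and be seen by the researchers. **Item 6.2** answers with an "automatic data cleaning process that ensures that all names and emails will be deleted from the database before any researchers have access".
- **Item 10.1**: "Participants will consent to their data from their user profile in TheMighty to be linked with their survey responses".
- **Item 12.6**: data are held first on the platform's encrypted servers and then moved to the university's servers.
- **Note after item 12.12**: fine geographic detail, with state given as one example, is an indirect identifier. IP address is not named there.

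**The concern.** The promise in Section 3 is absolute, but the data list in 5.23 contains fields that can help to identify a person, and the cleaning rule does not mention them. An investigator or programmer who built the export from 5.23 and 6.2 as written would remove names and emails and leave IP address and city in place.

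The sample makes this more than a matter of tidy wording. Under 7.2, participants qualify by reporting thoughts of suicide in the past 12 months, and the surveys in 5.1 and 5.2 ask about suicidal ideation and self-injurious thoughts and behaviors. A participant, or an ethics board, that relied on the Section 3 statement would believe the data flow to be better protected than 5.23 and 6.2 make it.

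**Working it through.** The documents give no figure on this point, so the check sets the statements side by side.

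1. **What is promised.** Section 3 excludes the sending of identity-compromising data at any time. The promise concerns sending, not only later storage or analysis.

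2. **What is listed.** Item 5.23 asks who provides which data, and the answer names the platform as the source. IP address and city, state and country come in the general list. Extra fields are mentioned only for registered users. Item 12.6 confirms a transfer from platform to university.

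3. **What is removed.** Two removal steps can be read:
   - 5.24: names, and only from the research analyses;
   - 6.2: names and emails, before researchers have access.

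   No readable text says that IP address or city is dropped, truncated or coarsened.

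4. **Whether the remaining fields are identifying by the form's own standard.** The note after 12.12 describes indirect identifiers as variables that may identify people when used together, and gives state of residence as an example. City is finer than state, and 5.24 places location beside age, gender and prior activity. Location therefore meets the form's definition without help from IP address.

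5. **Whether these fields are joined to the sensitive answers.** Item 10.1 joins user-profile data to survey responses. Item 5.24 counts geographical location among the account variables, so linkage of location is supported, although 5.24 does not say at what level of detail. IP address appears in 5.23 but not among the account variables in 5.24, so its linkage to survey answers is an inference.

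6. **Whether the risk section covers the fields.** The third risk in 6.1 is limited to user names and emails, and the cleaning step in 6.2 matches that risk. IP address and location are not assessed in either item.

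7. **Whether the analysis needs the fields.** The four SAP hypotheses use group, day of survey, history of suicidal thoughts, days of participation, desire to die, optimism and connectedness. None uses IP address or location. A plausible use is detection of repeat enrolment, which 9.3 shows to be a worry.

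8. **How many people.** Section 5.1 plans 50 in the feasibility trial and 500 in total in the research trial; 7.1 plans 50 and 1,000. Potential exposure is therefore 50 + 500 = 550 or 50 + 1,000 = 1,050 participants.

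**The case against.** The best reply is that much of the protocol's protection cannot be read. The ticks at 5.22 (identifiability of existing data), 12.1 to 12.3 (identifiability when obtained and stored, security level) and 12.12 (fate of identifiers) are missing from the available text. The chosen options may include coding, or removal by the research team on receipt. This limits what can be concluded. A reader might infer that the protocol offers no protection beyond deleting names and emails; the documents do not support that. The contradiction nevertheless stands: if the team removed identifiers on receipt, they would already have been sent, which Section 3 says will not happen.

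Three other stronger readings are tempting and should be resisted.

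- **That IP addresses will reach the researchers attached to suicidality ratings.** No item says so. Item 5.23 belongs to a section on previously collected data, and the linkage statement in 10.1 names profile data only.
- **That the cleaning step fails against the risk the protocol states.** It does not. The stated risk concerns user names and emails, and the step addresses exactly those. The fair criticism is that the stated risk is too narrow.
- **That participants will be traced.** Re-identification is possible from the fields listed, but nothing in the documents shows that it would occur.

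There are also real mitigations. Only consenting participants' secondary data are used (5.26), profile linkage is by consent (10.1), and the platform's servers are encrypted (12.6). These lower the risk, but they neither reconcile Section 3 with 5.23 nor widen the cleaning step.

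**Conclusion.** The point holds as an internal contradiction with a practical consequence. Section 3 rules out sending data that may compromise identity, 5.23 lists IP address and city among the data supplied, and no readable safeguard covers either. Location is an indirect identifier by the form's own definition, and its linkage to survey answers is supported by 10.1 together with 5.24.

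The potential exposure is 550 or 1,050 participants, depending on which planned size applies. There is no effect on any estimate, on power or on the SAP's analyses. The conclusion assumes that 5.23 describes what is actually transferred, and that none of the unreadable tick boxes records a removal of these fields before transfer. It should be corrected before data are exported, but it does not threaten the trial's findings.

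**What to change.** 1. Extend the automatic cleaning step in 6.2 so that the platform removes IP address and any location finer than country before transfer. Keeping state would not be enough, because the form's note lists state as an indirect identifier.
2. Have the platform run any duplicate-enrolment check and pass on only a flag.
3. Correct 5.23 to list only the fields transferred. Age, gender, articles viewed and site activity are not touched by this filter, so the corrected list should say openly which of them remain.
4. If IP address or finer location is needed, take the other route: amend the Section 3 statement so that it no longer makes an absolute promise, and add indirect identifiers to the risks in 6.1 and the safeguards in 6.2.

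The cost is some protocol wording and one extra filter in the platform's export. The downside is small: researchers could not run their own IP-based duplicate check or describe the sample's location below country level. No SAP analysis would change.
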